
Planned Number of Subjects
	
Up to 3750 subjects will be enrolled. An interim analysis is planned to determine final sample size.

Planned Number of Sites / Countries
	
Up to 200 sites in the United States, Canada, Europe and Asia Pacific.

Primary Safety Endpoint
	
This is a post-market study with no primary safety endpoint.

Primary Effectiveness Endpoint
	
This is a post-market study with no primary effectiveness endpoints.

Additional Endpoints
	
This is a post-market study with no secondary endpoints.

Method of Assigning Patients to Treatment
	
There is no randomization as all subjects are assigned to a single group and are followed with HeartLogic disabled. The investigator will have access to an electronic database which will be used to generate the patient ID and all eCRFs for subjects enrolled in the clinical study.

Follow-up Schedule
	
The required protocol study visits and medical record reviews are as follows:
 
 
• Enrollment visit
 
• Baseline visit
 
• Interim medical record review (6 month, does not require a clinic visit)
 
• Final clinic visit (12 month, or at the point of withdrawal)
 
 
Subjects will exit the study following their final clinic visit.

Study Duration
	
The study duration is estimated to be 6 years from first patient enrollment to study closure.

Participant Duration
	
The study duration for each subject is expected to be approximately 12 months from enrollment to the final clinic visit. A patient can be in the study for up to 460 days (15 months) if the maximum visit windows are taken in to account.

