### ***6.3 Treatment and Control***

This is an observational study with no treatment or control groups. All enrolled subjects will already be implanted with a commercially available Boston Scientific CRT-D or ICD device. For the specific model numbers see Table 4-1. Devices will have Heart Failure Sensors turned ON, Respiratory Sensor turned ON, Sleep Incline Sensor turned ON, and HeartLogic disabled.

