### **10.3 Other Objectives/Measurements**

The additional objectives are described below along with planned statistical methods and analysis data to be used.

- Characterize HF sensors for the association with risk for VT/VF therapy
  - This will be assessed using an odds ratio
  - All subjects with usable sensor and episode data will be included in the analysis
- Characterize HF sensors for phenomapping of HF events
  - This will be assessed using cluster analysis
  - All subjects with a HF event and usable sensor data will be included in the analysis
- Characterize HF sensors for association with non-HF hospitalizations (including cardiac non-HF events and non-cardiac events)
  - This will be assessed using a paired t-test
  - All subjects with a non-HF hospitalizations and usable sensor data will be included in the analysis
- Collect Sleep Incline Sensor data leading up to clinical events: Subjects who were enrolled in a remote monitoring program using sleep incline data will be excluded and sensor data in the remaining patients will be analyzed using a paired t-test.
- Link study data to third-party data sources. Data linkage will be included in the analysis to assess feasibility to link to claims data (see Section 9.5) and other data sources. The linked data set will be used to compare claims-based events with study RCEs, assess the accuracy of claims-based algorithms to identify sensor detected events, and estimate the cost savings from avoidable hospitalizations. Comparisons will be made using paired and un-paired t-tests and receiver operator curve (ROC) analyses.

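### Section 10.3 names t-tests and ROC for all linkage aims, but neither shows whether claims and study records captured the same events, and the cost saving can only be a projection

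*Protocol*

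**What the plan says.** The last item of Protocol Section 10.3 covers linkage to third-party data. It lists four uses:

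- feasibility of linkage: "Data linkage will be included in the analysis to assess feasibility to link to claims data";
- event comparison: "The linked data set will be used to compare claims-based events with study RCEs";
- algorithm accuracy: "assess the accuracy of claims-based algorithms to identify sensor detected events";
- economics: "estimate the cost savings from avoidable hospitalizations".

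One closing sentence supplies the methods: "Comparisons will be made using paired and un-paired t-tests and receiver operator curve (ROC) analyses". It does not say which method serves which use.

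On design, the synopsis (Method of Assigning Patients to Treatment) says that "all subjects are assigned to a single group and are followed with HeartLogic disabled", and Section 6.3 says "This is an observational study with no treatment or control groups". Sections 10.1 and 10.6 call the study exploratory, with no formal hypothesis tests and no multiplicity adjustment.

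**The concern.** RCEs are discrete, dated events: all-cause hospitalizations and heart failure outpatient visits (Section 5.1). Comparing them with claims raises two questions: how many study events also appear in claims, and how many claims events are real. Of the printed methods, the t-tests address neither, because missed events and spurious ones cancel in a difference of means. ROC analysis addresses the first in part, for an algorithm with a graded output. It does not give PPV, which also depends on how common events are, and it does not measure event-level agreement.

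The cost aim has a different difficulty. With one group, the feature disabled and no comparator, the data contain hospitalizations that happened and none that were seen to be averted by acting on the sensors. A t-test or an ROC curve on such data gives no saving until someone supplies the fraction that could have been averted.

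At stake is how the linkage results are read. A comparison of means could look reassuring while the two sources record different events, and a projected saving could be reported as if the study had measured it.

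**Working it through.** The protocol gives no figure for the linkage objective, so there is none to reproduce. The 215, 270 and 3750 of Section 10.1.2 belong to the primary objective and do not enter here. The numbers below are illustrations; only the 9% is borrowed from the protocol.

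**1. What a paired t-test on event occurrence measures**

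For N subjects, let a = event in both sources, b = study only, c = claims only, d = neither. The mean paired difference is (b − c)/N, so the test looks only at the imbalance between b and c.

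- Sensitivity of claims = a/(a + b)
- PPV of claims = a/(a + c)
- Kappa = (Po − Pe)/(1 − Pe), where Po is observed and Pe is chance agreement

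**2. Equal totals, moderate overlap**

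Assume N = 1,000, 279 subjects with an event in each source, and 168 in both. Then a = 168, b = 111, c = 111, d = 610.

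- Mean difference = (111 − 111)/1,000 = 0, so t = 0 and p = 1
- Sensitivity = 168/279 = 0.602; PPV = 168/279 = 0.602
- Po = (168 + 610)/1,000 = 0.778
- Pe = 0.279² + 0.721² = 0.0778 + 0.5198 = 0.5977
- Kappa = (0.778 − 0.5977)/(1 − 0.5977) = 0.448

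**3. Better linkage, unequal totals**

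Keep 279 study events, let claims capture about 90% of them (251), and assume no spurious claims events. Then a = 251, b = 28, c = 0, d = 721.

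- Mean difference = 28/1,000 = 0.028
- Variance of the differences = (28 − 1,000 × 0.028²)/999 = 27.216/999 = 0.02724
- t = 0.028/√(0.02724/1,000) = 5.36
- Sensitivity = 251/279 = 0.90; PPV = 251/251 = 1
- Po = 0.972; Pe = 0.279 × 0.251 + 0.721 × 0.749 = 0.6101; kappa = 0.3619/0.3899 = 0.93

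The t-test signals a difference for the better linkage and none for the worse one.

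**4. Same behaviour with sampling variation**

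Assume 3,000 subjects, 9% with an event (the rate in Section 10.1.2, used only as a plausible prevalence), and expected false positives equal to expected misses. Each row is 1,000 simulated data sets.

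| Sensitivity = PPV | Mean kappa | Paired t-test rejects |
|---|---|---|
| 0.9 | 0.89 | 6.4% |
| 0.7 | 0.67 | 5.2% |
| 0.5 | 0.45 | 4.9% |
| 0.3 | 0.23 | 5.6% |

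With equal prevalence p in both sources and sensitivity s, kappa = 1 − (1 − s)/(1 − p). At s = 0.3 and p = 0.09 this is 1 − 0.7/0.91 = 0.23, which agrees with the table. Agreement runs from good to poor while the rejection rate stays near its nominal 5%.

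**5. The cost aim**

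Let C be the claims cost of hospitalizations that followed a sensor change, and f the fraction of that cost that acting on the change would have averted. Gross saving = f × C. Linked data can supply C. With "There is no randomization as all subjects are assigned to a single group and are followed with HeartLogic disabled", they cannot supply f. The data limit f only to between 0 and 1, which is a logical bound and not an estimate of size.

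**The case against.** The strongest reply is that the methods sentence names ROC as well as t-tests and assigns neither to a particular use. ROC fits the algorithm-accuracy aim and yields sensitivity and specificity. T-tests are legitimate for mean events or mean costs per subject, paired between sources or un-paired between groups. All of this stands. A reader might infer from the section that the t-test is meant to decide whether claims and RCEs agree, or that the event comparison cannot be answered at all. The text supports neither: the first is only one possible pairing of method and aim, and the comparison is answerable in part.

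On cost, the protocol speaks of avoidable hospitalizations, not of hospitalizations avoided by HeartLogic. Costing potentially avoidable events is a modelling task that needs no enabled group, and Section 9.5.1 lists health economic evaluation among the purposes of linkage. A reader might infer that the aim is impossible in this design. It is not; what the design cannot give is an observed saving.

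A reader might also infer that linkage exists to let claims replace study-collected events. Section 9.5.1 gives broader research purposes. Section 3.1 frames the aim as feasibility, and its remark about evaluating device features without expensive trials is background.

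Finally, matching windows and interval methods are commonly left to the SAP, which is not at hand, and the objective is exploratory. That stands as far as missing detail goes. It does not remove the point, because 10.3 does print the methods and the printed set does not include a measure of event agreement. Exploratory status excuses the lack of hypotheses, not a statistic that answers a different question.

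**Conclusion.** The point holds in a limited form. For claims events against RCEs, the t-tests in 10.3 compare mean rates and cannot show whether the same events were recorded. ROC covers graded algorithms but gives neither PPV nor event-level agreement. The cost figure cannot be observed in this design and is a projection resting on an averted fraction from outside the study.

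The size of any effect on the results cannot be estimated from the protocol. The examples assume the overlap and the event totals. In the first, t = 0 follows from setting the totals equal. They show what the test cannot see, not how well claims will perform here. With offsetting errors, kappa anywhere from 0.23 to 0.89 gave the same rejection rate of about 5 to 6%.

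This is a minor point on an exploratory objective. It does not touch the primary objective, the sample size or the data collection.

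**What to change.** In Section 10.3, assign methods to aims:

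- **Claims events versus RCEs:** match events within a stated date window and report sensitivity, PPV and kappa, with confidence intervals that account for clustering of events within subjects. Matching dated events leaves no count of joint non-events, so compute kappa per subject or per fixed interval of follow-up.
- **Mean event counts or costs per subject:** keep the paired and un-paired t-tests.
- **Claims-based algorithms with a graded score:** keep ROC analysis.
- **Cost:** restate the aim as the cost of hospitalizations preceded by a sensor change. This is an upper bound on the hospitalization cost that acting on sensor changes could save. Show any averted fraction as an assumed range and label the result a modelled projection.

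The change is to wording only and needs no new subjects or data items. Section 10.13 allows it to be documented in the SAP if that is approved before the analyses. The cost is that the economic aim becomes more modest.

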#### ***10.4 General Statistical Methods***

All sample size calculations were performed and all statistical analyses will be done with SAS version 9.3 or higher.

#### ***10.5 Analysis Sets***

##### **10.5.1 Primary analysis**

All subjects with a usable index HF hospitalization and all subjects with a 30-day HF readmission will be included in the primary analysis. Subjects with a 30-60-day HF hospitalization will be excluded from the analysis.

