Sample Size Parameters	
Up to 3750 enrolled subjects are necessary to evaluate the primary objective. An index HF hospitalization refers to the first HF hospitalization during the study follow-up period. A HF hospitalization is deemed usable if sensor data is available during the event and sufficient follow up time is recorded to determine if a readmission occurs.
 
A total of 215 usable index HF hospitalizations are required to have at least 80% power to detect a standardized difference of 0.5 in the mean sensor change (admission – discharge) between the groups with and without a 30-day HF readmission. It is expected that of the 215-usable index (first during the study) HF hospitalizations, 43 will be followed by a 30-day readmission (20%).
 
Based on the following assumptions, a total of 215 usable index HF hospitalizations are required:
 
 
• 80% Power to detect a standardized mean difference of 0.5 between groups
 
• Two-sided Type I error (alpha) of 0.05
 
• 3:1 ratio of group sizes (no-readmission:30-day HF readmission), where the no-readmission group will exclude index HF
 

	
hospitalizations with 31 to 60-day readmissions
 
Assuming a 20% loss of usable HF events due to proximity to study start and exit (completion or withdrawal), a total of 270 index HF hospitalizations are required to obtain 215 usable HF hospitalizations.
 
Based on the following assumptions, up to 3750 subject enrollments are required to obtain the 270 required HF hospitalizations:
 

• 9 % index HF hospitalization rate

• 20% death/withdrawal over entire length of the study

• Average of 12 months of sensor data per patient

--	--

2	Table of Contents	
1	PROTOCOL SYNOPSIS	8
2	TABLE OF CONTENTS	14
2.1	Table of Figures	18
2.2	Table of Tables	18
3	INTRODUCTION	19
3.1	Study Rationale and Background	19
4	COMMERCIAL DEVICE DESCRIPTION	21
4.1	Device Description	21
4.2	Medical Equipment Description	22
5	STUDY OBJECTIVES AND ENDPOINTS	24
5.1	Primary Objective	24
5.2	Study Endpoints	26
6	STUDY DESIGN	26

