### 5.1 Primary Objective

The primary objective of the PREEMPT-HF study is to investigate the association between HF Sensor data and 30-day HF readmissions.

Subjects will be followed for approximately 12 months to collect the required number of clinical events to support the study objectives. These events are called Reviewable Clinical Events (RCEs), and include all-cause hospitalizations and HF outpatient visits (as defined below).

[figure not shown]
RCEs require the investigational site to review the subject's medical records and complete the appropriate eCRF (Figure 3).

Clinical events for the purposes of data analysis are defined as follows:

- **Hospitalization (all-cause):** the subject is admitted to inpatient hospital care and discharged on a different calendar date.
- **HF Hospitalization:** the subject is admitted with signs/symptoms of congestive heart failure (CHF) and receives unscheduled augmented HF therapy with oral or intravenous medications, ultrafiltration therapy or other parenteral therapy.
- **HF Readmission (30-day):** the subject is admitted for an unplanned hospitalization for any cause within 30 days post discharge from a HF hospitalization.
- **HF Outpatient Visit:** the subject has signs/symptoms of congestive HF, and receives unscheduled intravenous decongestive therapy (e.g., IV diuretics, IV inotropes, IV vasoactive drugs, ultrafiltration), in a setting that does not involve a hospitalization (e.g.: emergency room, HF clinic, primary care clinic, etc.).

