#### 10.1.2 Sample Size

Approximately 3750 enrollments will be required for this study. The sample size was determined based on the estimated number of HF index hospitalizations and 30-day HF readmissions needed to evaluate the primary objective. Final sample size will be determined by an interim analysis as described in Section 10.9. An index HF hospitalization refers to the first HF hospitalization during the study follow-up period. A HF hospitalization is deemed usable if sensor data is available during the event and sufficient follow up time is recorded to determine if a readmission occurs.

A total of 215 usable index HF hospitalizations are required to have at least 80% power to detect a standardized difference of 0.5 in the mean sensor change (admission – discharge) between the groups with and without a 30-day HF readmission. It is expected that of the 215 index HF hospitalizations, 43 will be followed by a 30-day readmission (20%).

A total of 215 usable index HF hospitalizations was determined based on the following assumptions:

- 80% Power to detect a standardized mean difference of 0.5 between groups
- Two-sided type I error (alpha) of 0.05
- 3:1 ratio of group sizes (no-readmission : 30-day HF readmission), where the no-readmission group will exclude index HF hospitalizations with 31 to 60-day readmissions

Assuming a 20% loss of usable HF events due to proximity to study start and exit (completion or withdrawal), a total of 270 index HF hospitalizations are required to obtain 215 usable HF hospitalizations.

Approximately 3750 enrollments are required to obtain the 270 required index HF hospitalizations. This was determined based on the following assumptions:

- 9 % index HF hospitalization rate per patient year
- 20% death/withdrawal rate throughout duration of study
- Average of 12 months of sensor data per subject

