### **10.1.3 Statistical Methods**

The primary objective will be evaluated using an independent two sample t-test. A comparison of mean sensor value change (admission – discharge) will be made between the no-readmission group and the 30-day readmission group. All subjects with a usable index HF hospitalization and all subjects with a 30-day HF readmission will be included in the primary analysis. Subjects with a 31-60-day HF hospitalization will be excluded from the analysis. A two-sided alpha of 0.05 will be used.

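### The primary analysis set and the synopsis grouping are not tied to the usable index HF hospitalization on which the study was sized

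*Protocol*

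**What the plan says.** The primary comparison is a two-sample t-test of the admission-minus-discharge sensor change. It "will be made between the no-readmission group and the 30-day readmission group" (10.1.3). The next sentence of 10.1.3, repeated in 10.5.1, sets the population: "All subjects with a usable index HF hospitalization and all subjects with a 30-day HF readmission will be included in the primary analysis".

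Four other places bear on who that is:

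- Section 5.1 defines a 30-day HF readmission: "the subject is admitted for an unplanned hospitalization for any cause within 30 days post discharge from a HF hospitalization". The anchor is any HF hospitalization.
- Section 10.1.2 separates the index event from later ones: "An index HF hospitalization refers to the first HF hospitalization during the study follow-up period". An event is usable if sensor data exist during it and follow-up is long enough to tell whether a readmission occurs.
- The sizing in 10.1.2 and in the synopsis counts only index events. Of 215 usable index HF hospitalizations, 43 (20%) are expected to be followed by a 30-day readmission. Controls are index events too, "where the no-readmission group will exclude index HF hospitalizations with 31 to 60-day readmissions".
- The synopsis, under Statistical Test Method, compares subjects who had a 30-day HF readmission with those who did not, and does not mention the index event.

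**The concern.** A subject readmitted within 30 days of a usable index discharge is already covered by the first half of the inclusion sentence. The second half therefore adds people only if it reaches readmissions that follow some other HF hospitalization. No matching door is open to subjects who were not readmitted, so for the added subjects inclusion depends on the outcome.

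The synopsis raises a different problem, one of group assignment. A subject with a usable index event, no readmission after it and a readmission after a second HF hospitalization is already in the set through the first half of the sentence. Under the synopsis that subject is a case; under 10.1.2 the index event belongs to the no-readmission group. The protocol does not say which hospitalization supplies this subject's sensor change.

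Comparability is at stake. Either first events are compared with a mixture of first and later events, or the case group contains index events that no readmission followed.

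**Working it through.** **1. The plan's own figures.** Inputs from 10.1.2: standardized difference 0.5, two-sided alpha 0.05, 3:1 ratio, 20% readmission, 20% loss of usable events, 9% index rate per patient-year, 20% death or withdrawal.

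- Two-sample t-test with noncentrality d × √(n₁n₂/(n₁+n₂)): 42 + 126 gives 79.7% power and 43 + 129 gives 80.6%. So 43 cases and 3 × 43 = 129 controls are needed.
- 43/0.20 = 215. The remaining 215 − 43 − 129 = 43 are, by implication, the 31 to 60-day exclusions.
- 215/0.80 = 268.75, taken as 270; 3750 × 0.80 × 0.09 = 270.

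The chain reproduces, and every link counts index events. The first step works only if the 43 cases are a subset of the 215.

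**2. Who is where.**

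| Subject | 10.1.2 | 10.1.3 and 10.5.1, read literally | Synopsis grouping |
|---|---|---|---|
| Usable index, readmitted within 30 days of it | case | included | case |
| Usable index, no readmission by day 60, none later | no-readmission | included | no readmission |
| Usable index, no readmission by day 60, but one within 30 days of a later HF hospitalization | no-readmission | included by the first half | case |
| No usable index, readmitted after a later HF hospitalization | not counted | included by the second half | case |
| No usable index, never readmitted | not counted | not included | no readmission |

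Row 3 is the assignment conflict. Rows 4 and 5 together show the outcome-dependent inclusion.

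**3. How many.** The documents give no repeat HF hospitalization rate, so this is illustration only.

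- *Row 3, using the only rate in the protocol.* Assume 365 days of follow-up and an index day T uniform on 0 to 305, so that 60 days remain. The later hospitalization must fall after day T + 60 and leave 30 days to observe, a window of 275 − T days. Its mean is 275²/(2 × 305) = 124 days, or 0.340 years. At 9% per patient-year and 20% readmission: 129 × 0.09 × 0.340 × 0.20 = 0.8 subjects.
- *Row 3, assuming 10% have a later HF hospitalization.* 129 × 0.10 × 0.20 = 2.6. This needs about −ln(0.90)/0.340 = 0.31 events per patient-year, 3.4 times the protocol's rate.
- *Row 4, same 10%.* There are 270 − 215 = 55 non-usable index events, and 55 × 0.10 × 0.20 = 1.1.

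**4. Effect on power if 2.6 controls became cases.**

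- If their index change is used and resembles that of controls, the difference is 0.5 × 43/45.6 = 0.472. With 45.6 against 126.4, power is 77.5%.
- If their later change is used and carries the full 0.5, power is 82.1%.

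The direction cannot be told from the documents.

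**The case against.** The strongest reply is that there is no conflict. The sentence before the inclusion sentence in 10.1.3 names the two groups, so the inclusion sentence may simply list them again in loose words. The definition in 5.1 is a general event definition and was not written to assign subjects. The sizing plainly keeps cases inside the index events. This reading is reasonable, and on it the second half is redundant. It does not close the matter, because 10.5.1 is the section that defines the set and repeats the sentence without the group names.

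A second reply is that the synopsis problem does not come from the inclusion sentence at all. That is correct: those subjects enter through the first half in any case, so deleting the second half would not settle their group. This is why the fix needs an added sentence.

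Three stronger inferences are tempting, and the documents do not support them.

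- *Eleven extra cases.* A reader might apply 20% to the 55 non-usable index events: 55 × 0.20 = 11. But an observed readmission already settles the follow-up part of usability, so such an index event would normally fail only for missing sensor data. It then has no admission-minus-discharge value to enter the test. Also, 10.1.2 attributes the 20% loss to proximity to study start and exit, and an index event cut short by exit has no observed readmission.
- *Power falling to 68.2%.* This needs 129 × 0.40 × 0.20 = 10.3 reassigned controls. A 40% chance of a later HF hospitalization in the 0.340-year window implies about −ln(0.60)/0.340 = 1.5 events per patient-year, about 17 times the 9% rate. A higher rate after a first hospitalization is plausible, but nothing in the protocol supports that multiple.
- *A shift of 0.13 SD.* This combines the same 40% with an assumed 0.5 SD difference between later and first events, for which there is no source.

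**Conclusion.** The point holds as a wording conflict with two separate parts. Read literally, the inclusion sentence in 10.1.3 and 10.5.1 admits some subjects only because they were readmitted. Separately, the synopsis grouping and 10.1.2 can put the same usable-index subject in opposite groups. Neither matches the sizing on usable index events.

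Its size is unknown and probably a few subjects: about 1 to 3 through group assignment and about 1 through the inclusion sentence. These figures rest on assumed repeat rates between the protocol's 9% per patient-year and a 10% probability, with 20% of later events followed by a readmission.

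The sample size is not wrong, and no loss of power is shown. Importance is low, because 10.1, 10.1.1 and 10.6 describe an exploratory study without formal hypotheses or claims. It is still worth correcting, since this single comparison is the primary objective.

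**What to change.** In 10.1.3 and 10.5.1, delete the second half of the inclusion sentence, the part that admits every subject with a 30-day HF readmission. Add one sentence in both sections and in the synopsis: both groups are defined on the usable index HF hospitalization, readmission is counted within 30 days of discharge from that event, and the sensor change is taken from that same event. Report readmissions after later HF hospitalizations separately.

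The cost is a deletion in two places and one sentence in three. No new data are needed, and 43, 215, 270, 3750 and the 80% power stand. The small downside is that a few non-index cases leave the primary test. If the deleted words were meant only to name the groups, their deletion costs nothing.
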